3. HUMAN SUBJECTS

E1a. Human Subjects Characteristics:

The human subjects age range 16 - 30 yrs (inclusive) involved in this study will be - 40 BDD, 60 HRUD, 60 LRUD and 40 healthy control subjects matched as a group for age, gender and ethnicity who will be studied at baseline. BDD and UD subjects will be matched for depression severity at the time of the scan. However, it is likely that, by definition the BDD and UD subjects will be different in terms of other illness characteristics such as duration of illness, number of episodes, and history of alcohol and substance abuse. We will treat those illness variables as covariates in our statistical analysis (as described in section 2c(ii)1a above) to take into account the potential confounding effects of some of these variables.

Inclusion criteria for BDD patients:

1. Ages 15 - 30 years (inclusive) and able to give voluntary informed consent (consent will be taken from both parents and child for children under the age of 18)
2. Satisfy criteria for Diagnostic and Statistical Manual 4th edition (DSM-IV-TR) for Bipolar I or II disorder
3. Satisfy criteria for DSM-IV depressive episode-current
4. 17-item Hamilton Depression Rating Scale > 15 but < 25;
5. Young Mania Rating Scale score < 10
6. Satisfy criteria to undergo an MRI scan based on MRI screening questionnaire.
7. Able to be managed as outpatients during the study as ascertained by the following –
 - i. Clinical Global Severity Scale < 5 i.e. moderately ill;
 - ii. No significant suicidal or homicidal ideation or grossly disabled.

Inclusion criteria for All UD patients:

1. Ages 15 - 30 years and able to give voluntary informed consent (consent will be taken from both parents and child for children under the age of 18).
2. Satisfy criteria for DSM-IV-TR Major Depressive Episode using a Structured Interview
3. Never met criteria for mania or hypomania
4. 17-item Hamilton Depression Rating Scale score (HDRS) > 15 and < 25.
5. Young Mania Rating Scale (YMRS) score < 10
6. Satisfy safety criteria to undergo an MRI scan
7. Able to be managed as outpatients during the study as ascertained by the following –
 - i. Clinical Global Severity Scale < 5 i.e. moderately ill;
 - ii. No significant suicidal or homicidal ideation or grossly disabled

Additional Inclusion criteria for High Risk UD (HRUD) patients beside the inclusion criteria for UD:

These variables were chosen keeping in mind the most frequently cited risk factors for development of bipolar disorder in previous longitudinal studies of major depression

At least one of the following:

1. Family history of bipolar disorder in at least one first degree relative
2. History of any sub-threshold hypomania symptoms
3. History of mood episode related psychotic symptoms

Additional Inclusion criteria for Low Risk UD (LRUD) patients beside the inclusion criteria for UD:

These variables were chosen to minimize any overlap between the HRUD and LRUD groups.

1. No family history of BD in a first or a second degree relative
2. No past history of any sub-threshold hypomania symptoms
3. No history of psychotic symptoms

Exclusion criteria for UD and BDD patients:

1. Meeting DSM-IV criteria for schizophrenia, schizophreniform disorder, schizoaffective disorder, mental retardation, pervasive developmental disorder.
2. History of receiving electroconvulsive therapy in the past 1 year
3. Use of neuroleptics, mood stabilizers or benzodiazepines in the past 2 weeks.
4. Use of antidepressants in the past 2 weeks.
5. If on fluoxetine in the past, then should not have been on this medication for 5 weeks.
6. Acutely suicidal or homicidal or requiring inpatient treatment.
7. Meeting DSM-IV criteria for other substance/alcohol dependence within the past 6 months or abuse in the past 3 months, excluding caffeine or nicotine. The criteria will be evaluated by interview and urinary toxicology screening. The use of caffeine or nicotine will be recorded.
8. Use of alcohol in the past 1 week before the MRI scan.
9. No serious acute or chronic medical or neurological illness, including previously known HIV positive status (due to possible CNS involvement) as assessed by history, physical examination and laboratory examination including EKG, CBC and blood chemistry.
10. Current pregnancy or breast feeding.
11. Metallic implants or other contraindication to MRI.

Inclusion criteria for healthy subjects: Healthy subjects matched for age, gender and ethnicity will be included

1. Ages 15 - 30 years (inclusive) and able to give voluntary informed consent (consent will be taken from both parents and child for children under the age of 18)

2. No current or past history of psychiatric illness or substance abuse or dependence.
3. No current or past history of psychiatric illness or substance abuse or dependence in a first degree relative.

Exclusion criteria for healthy subjects:

1. Pregnant or breast feeding.
2. Metallic implants or other contraindication to MRI.
3. Significant family history of psychiatric or neurological illness.
4. Currently taking any prescription or centrally acting medications.
5. Serious acute or chronic medical or neurological illness as assessed by history, physical examination and laboratory examination including CBC and blood chemistry.
6. Use of alcohol in the past 1 week and not being able to avoid alcohol use during the course of the study.

E 1b. Potential Risks:

Risks associated with this study are those associated with the interview for psychiatric symptoms, venous blood drawing, MRI scan, potential delay in treatment, antidepressant treatment for UD patients, emergence of mania or hypomania, and loss of confidentiality.

E1b1. Interview for psychiatric symptoms: Some patients may become anxious when they focus on their symptoms.

E1b2 . Venous blood drawing for blood tests during screening: This can lead to pain and bruising at site. In rare cases inflammation or infection of the site can occur.

E1b3. MRI scan: There are almost no known significant physical risks associated with MRI. The only exceptions are individuals with certain surgical implants such as cardiac pacemakers. Subjects with such implants will be excluded from any study. A screening procedure will be used identical to that used for clinical MRI scanning. Subjects not passing the screening will be excluded from the study as being contraindicated for MRI. Subjects will be fully informed about the fMRI procedures with a written consent form. We will also show them pictures of the MRI machine and the visual apparatus so that they are fully aware of the procedures involved. Patients reporting previous experience of anxiety in closed spaces will be excluded.

E1b4. Delay in treatment: patients will only be included in the study if they are unmedicated at the time of initial screening. We will not do a medication wash-out for the purpose of this study. However, patients need to be kept off medication between screening and time of the scan. This may delay their treatment for a few weeks and worsen their depression. Patients may become suicidal or significantly impaired in terms of their functioning.

E1b5. Worsening of symptoms: Patients may have worsening of their symptoms during the waiting period before the first scan and during the study. Patients may become severely depressed and grossly disabled or may develop suicidal or homicidal ideation. Patients who become more manic may act impulsively and have poor judgment leading to self harm or harm others.

E1b6. Loss of confidentiality: There may be a loss of confidentiality of information obtained from psychiatric interviews and of the brain imaging data.

E1b7. Tolerability of fMRI procedures by psychiatric patients: Patients and healthy subjects may become uncomfortable or agitated during the scan. The procedures for fMRI and stimulus induced activation measurements have been used extensively in our radiology facilities. In the depression and bipolar study for which preliminary data has been provided patients tolerated the procedures very well. No patients' scan had to be interrupted midway due to patient's mental or physical discomfort. Other investigators at IUSM have used similar procedures with patients with schizophrenia and substance abuse disorders and the procedures have been well tolerated. The radiology imaging area is well staffed with personnel who have extensive experience in doing fMRI studies. A crash cart and other equipment and medical personnel for medical emergencies are also readily available. Throughout the procedures the patients comfort will be closely monitored and the study will be terminated if needed.

E1b8. Antidepressant treatment: Antidepressants are generally well tolerated. Common early side effects are nausea or stomach irritation, jitteriness and increased anxiety, changes in appetite,

constipation, dizziness, dry mouth, headache, increased sweating, taste changes, weight changes, sleep disturbances, sexual dysfunction, and possible increase in suicidal ideation. Antidepressants can also precipitate mania. In line with the purpose of the study, all subjects will be monitored closely every month for the first 6 months and every 3 months thereafter for two years or more frequently as needed and the medication stopped or changed if there are unwanted side effects. In high doses Wellbutrin may cause seizures, subjects with a history of seizures will not be treated with Wellbutrin.

E1b9 Antipsychotic Treatment: Although antipsychotic medication, such as risperidol, has been given to subjects with good results before, the study medication may cause some side effects. You may experience none, some, or all of those listed below. A common side effect for this type of drug when beginning treatment is sleepiness, dizziness, rapid heartbeat, dry mouth, constipation, indigestion, feeling weak, swelling of arms and legs, weight gain, fainting, blurred vision, increased appetite, pain in the arms and legs, hyperglycemia (high blood sugar), or stuffy nose. In some cases there may be a change in the amount of white blood cells (cells in your blood to help fight infections). If you experience symptoms such as fever and/or sore throat and sores on the tongue or inside of the mouth, you should seek medical care, as such symptoms may be due to a decrease in white blood cells. Some patients have shown an increase in the amount of liver enzymes (indicating possible liver injury or damage), other enzymes, or fatty substances in the blood. More uncommon side effects are allergic reactions and seizures. An allergic reaction to this drug might start with the following symptoms: itching or hives, swelling in your face or hands, swelling or tingling in your mouth or throat, chest tightness, or trouble breathing. A rare side effect is priapism (long-lasting and painful erection). Two very rare side effects that may occur with the use of quetiapine include neuroleptic malignant syndrome (NMS) and tardive dyskinesia. Neuroleptic malignant syndrome is a serious, potentially life-threatening disorder that includes symptoms such as high fever, tight muscles, changes in blood pressure and heart rate, or changes in thinking and understanding. If you appear to be developing neuroleptic malignant syndrome, your participation in the study will be stopped. Tardive dyskinesia is a syndrome of potentially irreversible, abnormal, involuntary movements of the tongue, jaw, body, arms, and legs. There is no known treatment for tardive dyskinesia, although the symptoms may lessen or disappear completely if the antipsychotic medication is stopped.

E2. Protection Procedures:

E2a. Recruitment and Informed Consent: BDD and UD patients will be recruited from patients presenting to the outpatient clinic at University Hospital, University counseling and Psychological Services, the Child and Adolescent Clinic at Riley Hospital, and by advertisement. Unmedicated BDD and UD patients frequently present to the mood disorders clinic at IUSM for first time diagnosis, or for consultation for whether they should be on medication or not. Unmedicated BDD or UD patients in a mood episode will be either in a moderate depression (BDD; HAM-D >15, < 25) There are a number of patients with mild to moderate forms of BD who present to our clinics or respond to advertisement who are not on medication.

To avoid any conflict of interest between the research and clinical missions of the Mood Disorders Clinic, patients who are in clinical treatment with [name] or [name] or in clinical treatment with another clinician supervised by them will only be recruited and consented to take part in the study by an independent clinician ([name]) not involved in the main study.

Patients in an unmedicated state who voluntarily wish to participate in the study will be recruited. Informed consent form approved by the Indiana University School of Medicine (IUSM) Investigational Review Board (IRB). For subjects under age 18 both parent and minor will sign the consent form. Subjects will have adequate time to read the consent form and make the decision to take part in the study by signing it. Subjects will be informed that their relationship with the treating clinic or the hospital will not be affected by whether they take part in the study or not. Subjects will take part in the study only after they have read and signed, in the presence of a witness, after being explained all the procedures of the study and had the opportunity to ask questions, the informed consent form approved by the IUSM IRB. Subjects will be given a copy of the signed

consent form and the original and copy will be kept for research records. Subjects will also be informed that they could terminate from the study at any time of their choice without affecting their relationship with the clinical staff or treating facility.

E2b. Protection against risk:

E2b1. Interview for psychiatric symptoms: experienced research personnel who will make every effort to minimize the subjects' apprehension will do the interview. Subjects will be clearly informed that they may stop the interview or not complete the tests at any time they choose. Subjects will also be informed that they can withdraw from the study at any time. In our experience, most subjects find going through their symptoms in detail helpful in understanding of their illness.

E2b2. Venous Blood draw for screening: a trained person who will make every effort to minimize pain or bruising will do Veni-puncture. If a subject has any of these complications then appropriate therapy will be instituted. The total amount of blood drawn in this study is around 10 cc or 1 tablespoon at the time of screening and 2 tablespoons on the day of the scan.

E2b3. MRI scan: A screening procedure will be used identical to that used for clinical MRI scanning. Subjects not passing the screening will be excluded from the study. Subjects will be fully informed about the fMRI procedures with a written consent form. We will also show them the MRI machine and the visual apparatus so that they are fully aware of the procedures involved. Patients reporting previous experience of anxiety in closed spaces will be excluded.

E2b4. Delay in treatment: Patients will only be included in the study if they are not on any psychotropic medications for at least 2 weeks at the time of the study. Therefore, there is no medications washout for the purposes of this study. Patients will undergo baseline ratings and MRI scans as soon as possible once they have been deemed to be eligible and have signed the consent form. From our experience of conducting the preliminary study we are usually able to arrange the baseline scan within a week once the patient is found to be eligible for the study and signs the consent form. Even in clinical settings, an evaluation period of 7 – 10 days is not uncommon before mild to moderately ill outpatients are started on medication. Subjects will be clinically assessed according to the criteria noted above, including lack of any significant suicidal or homicidal ideation and 17-item HAM-D score < 25, YMRS score < 10 and CGI severity score < 5 i.e., subjects will be judged to be only moderately ill. Patients will also be assessed regarding whether they can tolerate to continue as outpatients while not being on medications for 7 – 10 days. If not, then subjects will not be included in the study and either started on treatment at Indiana University Hospital or referred to the clinician of their choice. It is expected that most of the patients identified by the inclusion and exclusion criteria will be moderately ill depressed outpatients and they will not need inpatient treatment. However, once the patient is included in the study and their condition worsens, an option is available for them to be admitted into an inpatient research unit and treated clinically as described below. The P.I. has been conducting imaging studies with this category of patients for past 15 years and has considerable experience in safely getting patients through these studies.

E2b5. Worsening of symptoms before the baseline scan: Several steps will be taken for close monitoring of the patients during this study to prevent significant worsening of symptoms. First, we will not include patients with very severe symptoms as described above in E2b4, who are grossly disabled because of their mood symptoms or who have any significant suicidal ideation, intent or plan. Second, once the unmedicated patients are included in the study, they will be monitored closely with clinical visits every 3 days until the time that they have the first scan. Patients will be monitored at each visit with the (CSSRS). If patient's symptoms worsen, they will be monitored more frequently with the (CSSRS). They will be given emergency phone numbers with which they can contact either the principal investigator or a psychiatrist on the research team who will be available 24 hours, 7 days a week. If despite these interventions, at any time a patient's symptoms worsen by more than 10 points on the HAM-D or the YMRS, or significant worsening is judged by clinical evaluation e.g. suicidal ideation, the patient will be taken out of the study and treated clinically as necessary with pharmacotherapy and/or psychotherapy as an outpatient or hospitalized as an inpatient. An inpatient clinical as well as research unit is available at the participating hospitals to hospitalize patients if necessary. Patients will be followed up clinically as outpatients or inpatients until their condition is

improved and stabilized. At that point they will be referred to the clinician of their choice and referral will be arranged.

E2b6. Occurrence of hypomania or mania in UD patients during supervised antidepressant treatment phase and during follow-up: the development of subthreshold hypomania or full blown hypomania or mania are the endpoints for this study after which the subject will be terminated from the study and appropriate clinical treatment instituted and after stabilization the subjects will be referred to the treater of their choice. If a patient is deemed to require hospitalization it would be arranged at one of inpatient psychiatric units within the Indiana University School of Medicine. It should be noted that the risk of antidepressant induced mania has been reported only in BD I subjects and there is controversy regarding whether antidepressants can do the same in BD II disorder let alone in HRUD subjects⁷³. In any event, as discussed above, absent a firm diagnosis of BD based on past (hypo)manic symptoms clinically these patients cannot be started on lithium, anticonvulsants or atypical neuroleptics because of concern for side effects and the long-term nature of therapy. Therefore, HRUD subjects either get no treatment and needlessly continue to suffer from depression or more frequently they are treated with antidepressants in a clinical setting (as proposed in this application). However, close monitoring is advisable which the subjects will get in this study and which otherwise they may not get. We have elected to use selective serotonin reuptake inhibitors (SSRIs) or bupropion because there is some evidence that they are less likely to induce (hypo)mania.

E2b7. Treatment and Referral after the study: While the BD subjects is being screened and the fMRI scan being arranged and for the UD patients when they are coming to the end of the 24 months supervised treatment, we will start the process of identifying with the patients where they would like to be referred for treatment. A range of treatment options are available in the Indianapolis area including private university and other outpatient clinics and state hospital. We already have a handout available for all the addresses and phone numbers for patient to make an appointment which we routinely give to our research subjects after they finish the study with us. In this study, we will additionally call up the treater of the patient's choice and make sure that subjects will have an appointment. UD subjects will still be followed up every 3 months until the end of the study. As the patients included in this study will present as unmedicated because either they have never been diagnosed before or for some other reason elected not to take medication that was recommended (not an uncommon situation for many young patients) this process will help in patient complying and following through with treatment. In this way we will be able to get patients engaged in treatment which otherwise they are unlikely to get on their own.

E2b8. Loss of confidentiality: Documents which contain patient-identifying data will be kept in locked filing cabinets, with access restricted to authorized investigators participating in the research, and secretarial and administrative personnel who have been informed about the requirement to maintain confidentiality. Computer records that contain patient identifying data will be secured by passwords. Patients will not be identified in any reports or publications that may result from this study. University policies regarding HIPAA regulations for research subjects will be followed.

E2b9. Tolerability of fMRI procedures by psychiatric patients: Patients and healthy subjects may become uncomfortable or agitated during the scan. Subjects reporting symptoms of being uncomfortable in closed spaces will not be included in the study. The procedures for fMRI such as stimulus induced activation measurements have been used extensively in our radiology facilities. In the depression study and bipolar patients for which preliminary data has been provided patients tolerated the procedures very well. Other investigators at IUSM have used similar procedures with patients with schizophrenia and substance abuse disorders and the procedures have been well tolerated. The radiology imaging area is well staffed with personnel who have extensive experience in doing fMRI studies. A crash cart and other equipment and medical personnel for medical emergencies are also readily available. Throughout the procedures the patients comfort will be closely monitored and the study will be terminated if needed.

E2b10. Antidepressant treatment: Patients will be monitored and educated in detail for side effects of antidepressants. If a patient develops hypomania or mania they will be terminated from the

study and referred to the treater or their choice or in the worse case to an inpatient unit. The same will be done if the patient develops other unwanted side effects or desire treatment with another antidepressant or modality which cannot be provided in the study.

E2b11. Antipsychotic Treatment: Antipsychotics are generally well tolerated. All subjects will be monitored closely at each visit for any side effects. They will be given emergency phone numbers with which they can contact either the principal investigator or a psychiatrist on the research team who will be available 24 hours, 7 days a week.

E3. Potential benefits to subjects and others:

The risk/benefit ratio of the proposed study is favorable. The MRI is a routinely used medical procedure with little known harmful effects. In addition, the patients will have a thorough assessment for mood disorder and will have a better knowledge of how to get treatment for their illness. Subject's mental and physical state will be monitored closely and regular clinical treatment instituted immediately if subject's condition worsens and they cannot continue to participate in the study. Subjects will be compensated for their time to do the study and will be paid \$25 for the screening visit and \$75 for each MRI scan. UD subjects will also receive free treatment for the first 24 months of the study. They will also be paid \$25 for the first six months of study visits and \$50 for the remaining visits. The risk-benefit ratio of this study is quite low.

E4. Importance of knowledge to be gained

It is critical to be able to differentiate between unipolar depression (major depression or UD) and bipolar disorder depression (BDD). In particular, it is important to differentiate between bipolar II depression (hypomania without significant impairment of function and major depressive episodes) and UD. Understanding the neurobiology of why some patients only suffer from a depressive illness while others suffer from both (hypo)mania and depression is also critical in terms of understanding the etiology of these similar but at the same time very different illnesses. In addition, the ability to be able to make the correct diagnosis determines the type of treatment (mood stabilizers alone, antidepressants alone or a combination) indicated and has important implications in terms of long-term prognosis. Despite phenomenological and neurobiological research for past several decades, no single clinical or biological finding is available at present which can differentiate between the two illnesses. This study will investigate potential brain imaging markers for differentiating between the two groups. In the future, if reliable biomarkers are identified then it may be even be possible that a choice between antidepressants vs. mood stabilizers can be made at baseline and unwanted side effects and precipitation of mania can be avoided.

G. REFERENCES

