HYPOTHESIS 1: BDD subjects will be differentiated from UD and HC subjects on measures of resting state corticoamygdalar connectivity and task-induced activation: BDD subjects will have lower lateral orbitofrontal (LOFC)-amygdalar connectivity but higher ventral anterior cingulate cortex (vACC)-amygdalar connectivity compared to UD and HC subjects. On measures of activation, while performing a happy emotion NoGo-Go task, UD subjects will have less dorsal ACC (dACC) activation compared to BDD and HC subjects.

SPECIFIC AIM 2: To investigate similarities and differences between BDD, HRUD and LRUD on measures of corticoamygdalar connectivity and activation.

HYPOTHESIS 2: HRUD subjects will display a pattern of corticoamygdalar connectivity and task-induced activation which will have similarities and differences with both BDD and LRUD subjects: HRUD subjects will have lower LOFC-amygdalar connectivity similar to BDD subjects but also lower vACC-amygdalar connectivity similar to LRUD subjects. On measures of activation, on the happy emotion NoGo-Go task, HRUD and LRUD subjects would have a similarly decreased dACC activation but on a negative facial emotion recognition task both HRUD and BDD will have lower insula activation compared to LRUD subjects.

EXPLORATORY AIM 3: Ultimately, only prospective data regarding which patients actually develop BD can validate the ability of the baseline imaging measures to predict a BDD or UD diagnosis. The main indicator of bipolarity is the presence of hypo(manic) symptoms. Beside conversion to (hypo)mania we will also measure occurrence of episodes of sub-threshold hypomania symptoms using the Young Mania rating Scale (YMRS) and the mania syndrome checklist of the Schedule for Depression and Schizophrenia (MSC-SADS) which has been recently used to study hypomania development in depressed patients. Besides looking at differences between converters and non-converters, an analysis will also be conducted of the correlation between peak change of YMRS and MSC-SADS scores as well as the slope of the change for mania symptoms ratings obtained over the course of the two years of follow-up. The data could be used to plan future large scale definitive studies.

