where $h(t)$ is the hazard or rate of conversion at time (t), $h_0(t)$ is the baseline conversion rate and X_i for $i = 1, 2, \dots, p$ are covariates. The subjects will be followed in the fashion described in Table 3 with periodic assessments. The assumption of constant relative hazard rate over time will be tested and remedied if required following data transformation or by incorporating a piecewise constant hazard model. Based on this framework, we will test the significance of imaging and activation measures on the hazard rate. Our primary objective here is to identify those covariates that significantly affecting the hazard rate. The grouping of the UD (HRUD and LRUD) will be also treated as a separate covariate and put in the model as an indicator variable. To detect the progression of disease severity (episodes of (sub) threshold hypo(mania)) we will additionally use Young Mania Rating Scale (YMRS) and the mania syndrome checklist from the Schedule for Depression and Schizophrenia (MSC-SADS) between study visits over during follow-up. We will test the group difference between LRUD and HRUD using mixed-effects linear regression analyses⁹⁷ with repeated measurements taken over two years. Each model will include a random intercept and slope and fixed effects group, and time, as well as the stratification covariates. A likelihood ratio test will examine the incremental contribution of the group effect over time.

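### Past sub-threshold hypomania separates HRUD from LRUD and is also what Aim 3 scores; the imaging correlations with those scores need the group and entry-criterion terms the plan does not state

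*Combined protocol and SAP*

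**What the plan says.** **Selection (section E1a).** HRUD requires "At least one of the following": a first-degree relative with bipolar disorder, "History of any sub-threshold hypomania symptoms", or psychotic symptoms linked to a mood episode. LRUD requires, among other things, "No past history of any sub-threshold hypomania symptoms". The separation is deliberate: "These variables were chosen to minimize any overlap between the HRUD and LRUD groups". Every UD subject must also enter with "Young Mania Rating Scale (YMRS) score < 10".

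**Outcome (Statistical Analysis, Specific Aim 3).** YMRS and MSC-SADS are used to pick up episodes of sub-threshold or threshold hypomania during follow-up, under the label of disease progression. Then: "We will test the group difference between LRUD and HRUD using mixed-effects linear regression analyses". On the terms: "Each model will include a random intercept and slope and fixed effects group, and time, as well as the stratification covariates". The stratification covariates are not named. Section E2b6 also counts sub-threshold hypomania among the study's endpoints.

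**Imaging (Exploratory Aim 3 and Exploratory Hypothesis 3).** Peak change and slope on the two scales are to be correlated with four baseline measures: LOFC-amygdala connectivity and posterior insula activation (negatively), vACC-amygdala connectivity and dACC activation (positively). No group term is stated for these correlations. The Cox model for conversion does carry an HRUD/LRUD indicator. The covariate list under Adjusting for covariates does not name prior sub-threshold hypomania.

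**The concern.** One construct serves as both a selection variable and an outcome. This raises two questions.

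1. **Meaning of a group difference.** If subjects with past sub-threshold symptoms have such symptoms again, HRUD will score higher than LRUD. That need not mean that anyone is moving toward bipolar disorder, or that family history or psychosis carries risk. The entry limit on YMRS restricts current symptoms, not history, so a later episode still registers as change from a low baseline.
2. **Meaning of a pooled correlation.** If HRUD and LRUD differ both on the scale and on an imaging measure, pooling them produces a correlation even when imaging predicts nothing within either group. For LOFC this spurious correlation has the hypothesised sign.

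The plan says that Aim 3 data could be used to plan later definitive studies, so either misreading would carry forward.

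**Working it through.** **The plan's own figure.** Sample size and power claims 90% power for the HRUD-LRUD contrast on the scales with 60 per group and 20% attrition, i.e. 60 × 0.8 = 48 per group. The text gives no mean difference or SD, so this cannot be reproduced. Inverting the two-sided two-sample formula, d = (1.96 + 1.28) × √(2/48) = 0.66 SD is what the claim implies.

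**Inputs for the correlation check**
- n: 48 per group, 96 pooled.
- Imaging difference dI: the plan gives -0.254 for left LOFC-amygdala connectivity, HRUD against LRUD, without stating the scale. Read as standardised, dI = 0.254. The stated 88% power at 60 per group instead implies (1.96 + 1.175) × √(2/60) = 0.57. Both are used.
- Share q of HRUD with past sub-threshold symptoms: not in the documents; assumed 25%, 50%, 75%.
- Shift D in later score for those subjects: not in the documents; assumed 0.5 and 1.0 SD. A score level stands in for peak change or slope.
- No relation between imaging and score within any subset.

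**Formula.** The group score difference is q × D, at most 0.75 × 1.0 = 0.75 SD. With equal groups:
- covariance = -0.25 × dI × qD
- variance of imaging = 1 + 0.25 × dI²
- variance of score = 1 + 0.5 × q(1-q)D² + 0.25 × (qD)²

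Top corner, dI = 0.57, q = 0.75, D = 1.0: covariance = -0.107; variances 1.081 and 1.234; r = -0.107/√(1.081 × 1.234) = -0.093. The test statistic centres on 0.093 × √93 = 0.89, so the chance of p < 0.05 is about 14-15%.

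Same corner with dI = 0.254: r = -0.048/√(1.016 × 1.234) = -0.043; the statistic centres on 0.41, giving about 7%.

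**Simulation (40,000 runs per cell), pooled correlation, rate of p < 0.05**

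| q | D | dI = 0.254 | dI = 0.57 |
|---|---|---|---|
| 25% | 0.5 | 5.2% | 5.2% |
| 25% | 1.0 | 5.3% | 6.0% |
| 50% | 0.5 | 5.3% | 6.2% |
| 50% | 1.0 | 5.9% | 9.4% |
| 75% | 0.5 | 5.6% | 7.7% |
| 75% | 1.0 | 6.7% | 14.6% |

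With dI = 0 the rate is about 5% in every cell. After adjusting for group it is about 5% in every cell.

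**Which measures are exposed.** Hypothesis 2 predicts that HRUD and LRUD differ on LOFC-amygdala connectivity and insula activation. It predicts that they are alike on vACC-amygdala connectivity and dACC activation. On the plan's own hypotheses, two of the four correlations are exposed.

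**Is a group term enough?** Not always. In a further simulation, imaging depended only on family history and the outcome only on prior symptoms (1 SD each). The group-adjusted test rejected in 7-10% of runs, with mean r about +0.05, because meeting any one criterion admits a subject and so links the criteria within HRUD. This favours adjusting for the criteria themselves.

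**The case against.** - **Contrasting risk groups is the design.** The HRUD criteria are presented as the most frequently cited risk factors, and past history is not the same variable as prospective follow-up. This stands. A reader might infer that the HRUD-LRUD test is circular or invalid; the documents do not support that. Sub-threshold history is one of three alternative routes, its share is not given, and the outcome is measured later. The overlap limits interpretation only.
- **The group-difference rates are not error rates.** Under the assumptions above, the group test is significant in about 9% (25% share, 0.5 SD) to 94% (75% share, 1.0 SD) of trials. That is power to detect a real, assumed difference in later scores. It shows that recurrence could produce a positive result, not that the type I error is inflated. This stands.
- **The outcomes are changes.** A stable elevation would largely cancel in peak change and slope, and the mixed model has a random intercept. This stands for a constant trait. Episodic recurrence would still raise peak change, but that mechanism was not simulated separately.
- **Aim 3 is exploratory.** Its stated primary objective is the hazard model, which already carries the group indicator. This stands and lowers the weight of the point. It also shows that the authors accept the adjustment in one model and leave it unstated in its neighbour.

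**Conclusion.** The overlap between selection and outcome is plain in the text, and nothing in the plan separates recurrence from progression. For the scale comparison the consequence is one of labelling: a difference carried by the sub-threshold-history route cannot be read as progression.

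For the imaging correlations there is a statistical consequence, but a modest one: a false-positive rate of about 5-7% at an imaging difference of 0.254 SD and about 5% to 14-15% at 0.57 SD, against about 5% with group adjustment. This rests on the assumed share (25-75%) and shift (0.5-1.0 SD), and on 48 analysed per group.

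A reader might infer that selection alone creates the correlation. It does not: imaging must also differ between the groups and the analysis must ignore group. Nor do higher rates follow within the assumed range. A rate of 22-23% at 0.57 SD needs a 1.0 SD difference between whole groups; with a shift of at most 1.0 SD, that means every HRUD subject entering by this route.

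**What to change.** 1. In the Exploratory Hypothesis 3 analyses, include HRUD/LRUD and the three entry criteria (family history, prior sub-threshold hypomania, psychotic symptoms) as prespecified covariates, outside the stepwise selection. Alternatively, report within-group partial correlations. Record all three criteria for every HRUD subject, not only the qualifying one. If no HRUD subject meets more than one criterion, the group indicator equals the sum of the three and must be dropped.
2. Keep the full HRUD-LRUD comparison on YMRS and MSC-SADS as planned, and add a sensitivity analysis by entry criterion.
3. State in advance that a difference confined to the sub-threshold-history route will be described as recurrence, not progression.

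**Cost.** A few model degrees of freedom and some wording; the criteria are established at screening. The sensitivity analysis has less power. Leaving out HRUD subjects with sub-threshold history leaves 12 to 36 of 48 at the assumed shares. At d = 0.66, power is then about 52% (12), 74% (24) or 84% (36), against 89% for 48 per group. For that reason the restricted comparison should not replace the main one.
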